### **8.3.2 Analysis of Treatment Emergent Clinical Laboratory**

Subject incidence of hematologic toxicities for platelet counts, hemoglobin, and neutrophils, graded per IWCLL 2008 guideline and CTCAE, will be summarized by treatment arm and grade.

The treatment emergent laboratory abnormality is defined as laboratory abnormality reported during the treatment emergent period (defined in Section 6). Treatment emergent laboratory abnormality, per NCI CTCAE v4.03 grading, will be summarized for hematology and chemistry laboratory parameters of clinical interest.

Shift from baseline grade to maximum post-baseline CTCAE grade will be summarized for hematology and chemistry laboratory parameters of clinical interest.

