5 SELECTION OF SUBJECTS

5.1 INCLUSION CRITERIA

Eligible subjects will be considered for inclusion in this study if they meet all of the following criteria:

1. Men and women ≥ 18 years of age.
2. ECOG performance status of 0 to 2.
3. Diagnosis of CLL that meets published diagnostic criteria ([Hallek 2008](#)):
 - a. Monoclonal B-cells (either kappa or lambda light chain restricted) that are clonally co-expressing ≥ 1 B-cell marker (CD19, CD20, or CD23) and CD5.
 - b. Prolymphocytes may comprise $\leq 55\%$ of blood lymphocytes.
 - c. Presence of $\geq 5 \times 10^9$ B lymphocytes/L (5000 μL) in the peripheral blood (at any point since diagnosis); this applies to CLL only.
4. Must have ≥ 1 of the following high-risk prognostic factors:
 - a. Presence of 17p del by central laboratory.
 - b. Presence of 11q del by central laboratory.
5. Active disease meeting ≥ 1 of the following IWCLL 2008 criteria for requiring treatment:
 - a. Evidence of progressive marrow failure as manifested by the development of, or worsening of, anemia (hemoglobin < 10 g/dL) and/or thrombocytopenia (platelets $< 100,000/\mu\text{L}$).
 - b. Massive (ie, ≥ 6 cm below the left costal margin), progressive, or symptomatic splenomegaly
 - c. Massive nodes (ie, ≥ 10 cm in the longest diameter), progressive, or symptomatic lymphadenopathy.
 - d. Progressive lymphocytosis with an increase of $> 50\%$ over a 2-month period or a LDT of < 6 months. LDT may be obtained by linear regression extrapolation of ALC obtained at intervals of 2 weeks over an observation period of 2 to 3 months. In subjects with initial blood lymphocyte counts of $< 30 \times 10^9/\text{L}$ (30,000/ μL), LDT should not be used as a single parameter to define indication for treatment. In addition, factors contributing to lymphocytosis or lymphadenopathy other than CLL (eg, infections) should be excluded.
 - e. Autoimmune anemia and/or thrombocytopenia that is poorly responsive to standard therapy.
 - f. Constitutional symptoms documented in the subject's chart with supportive objective measures, as appropriate, defined as ≥ 1 of the following disease-related symptoms or signs:
 - i. Unintentional weight loss $\geq 10\%$ within the previous 6 months before Screening.
 - ii. Significant fatigue (ie, ECOG performance status 2 or worse; inability to work or perform usual activities).

- iii. Fevers > 100.5°F or 38.0°C for ≥ 2 weeks before Screening without evidence of infection.

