 - iv. Night sweats for > 1 month before Screening without evidence of infection.
6. Must have received ≥ 1 prior therapies for CLL.
8. Meet the following laboratory parameters:
 - a. ANC ≥ 750 cells/μL ($0.75 \times 10^9/L$) or ≥ 500 cells/μL ($0.50 \times 10^9/L$) in subjects with documented bone marrow involvement, and independent of growth factor support 7 days before assessment.
 - b. Platelet count ≥ 30,000 cells/μL ($30 \times 10^9/L$) without transfusion support 7 days before assessment. Subjects with transfusion-dependent thrombocytopenia are excluded.
 - c. Serum AST/SGOT and ALT/SGPT ≤ 3.0 x ULN.
 - d. Total bilirubin ≤ 1.5 x ULN.
 - e. Estimated creatinine clearance (ie, eGFR using Cockcroft-Gault) ≥ 30 mL/min.
9. Able to receive all outpatient treatment, all laboratory monitoring, and all radiologic evaluations at the institution that administers study drug for the entire study.
10. Women who are sexually active and can bear children must agree to use highly effective forms of contraception while on the study and for 2 days after the last dose of acalabrutinib or 90 days after the last dose of ibrutinib, whichever is longer. Highly effective forms of contraception are defined in [Section 6.2.11](#).
11. Men who are sexually active and can beget children must agree to use highly effective forms of contraception during the study and for 2 days after the last dose of acalabrutinib or 90 days after the last dose of ibrutinib, whichever is longer. Highly effective forms of contraception are defined in [Section 6.2.11](#).
12. Men must agree to refrain from sperm donation during the study and for 2 days after the last dose of acalabrutinib or 90 days after the last dose of ibrutinib, whichever is longer.
13. Must be willing and able to adhere to the study visit schedule, understand and comply with other protocol requirements, and provide written informed consent and authorization to use protected health information (in accordance with national and local patient privacy regulations). Note vulnerable subjects, as defined in the International Conference on Harmonisation (ICH) GCP, are not allowed on this protocol (eg, prisoners or institutionalized subjects).

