Appendix E: Hematologic Adverse Event Grading Scheme (Hallek 2008)

An evaluation of the hematologic toxicity in subjects with advanced CLL must consider the high frequency of marrow involvement and previous exposure to chemotherapy with consequent medullary compromise at the initiation of therapy. The standard hematologic grading system for solid tumors cannot, therefore, be directly applied. A substantial proportion of subjects would be considered to have Grade 2 to 4 hematologic toxicity before any therapy is given. Therefore, the following modified schema will be used to quantitate hematologic deterioration in subjects with CLL.

Hematologic Grading Scheme

Grade ¹	Decrease in platelets ² or Hb ³ (nadir) from pretreatment value	Absolute neutrophil count/ μL ⁴ (nadir)
0	No change to 10%	≥ 2000
1	11%-24%	≥ 1500 and < 2000
2	25%-49%	≥ 1000 and < 1500
3	50%-74%	≥ 500 and < 1000
4	$\geq 75\%$	< 500

- Grades: 1, mild; 2, moderate; 3, severe; 4, life-threatening; 5, fatal. Death occurring as a result of toxicity at any level of decrease from pretreatment will be reported as Grade 5.
- Platelet counts must be below normal levels for Grades 1 to 4. If, at any level of decrease, the platelet count is $< 20 \times 10^9/\text{L}$ ($20,000/\mu\text{L}$), this will be considered Grade 4 toxicity, unless a severe or life-threatening decrease in the initial platelet count (eg, $< 20 \times 10^9/\text{L}$ [$20,000/\mu\text{L}$]) was present pretreatment, in which case the patient is not evaluable for toxicity referable to platelet counts.
- Hemoglobin (Hb) levels must be below normal levels for Grades 1 to 4. Baseline and subsequent Hb determinations must be performed before any given transfusions. The use of erythropoietin is irrelevant for the grading of toxicity, but should be documented.

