#### **4.1.6 Treatment Emergent Period**

The treatment emergent period is defined as the period of time from the date of the first dose of study drug through 30 days after the date of the last dose of study drug or the first date starting new anticancer therapy for CLL, whichever is earlier.

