### **8.1.1 Treatment Emergent Adverse Events**

TEAE is defined as an adverse event reported during the treatment emergent period (defined in Section 4.1.6). Any ongoing event that worsens in severity after the first dose date of study drug is also defined as a TEAE. Incomplete onset dates will be imputed as detailed in Section 4.2, for the purpose of determining whether AEs are treatment emergent.

TEAEs will be tabulated in summary tables by treatment arm. For each treatment arm, frequency and percentage of adverse events within each system organ class and preferred term will be presented. The denominator for the adverse event incidence will be based on the number of safety population subjects in that treatment arm, unless otherwise specified. Adverse event incidence rates will also be summarized by severity and relationship to study drug based on the investigator’s judgment.

Subjects with multiple occurrences of events for a given preferred term, system organ class, or overall will be counted only once at the maximum severity and strongest relationship to study drug, respectively, for each preferred term and system organ class.

In addition, Grade 3 or Grade 4 TEAEs, TEAEs that led to permanent study drug discontinuation, TEAEs that led to dose reduction, TEAEs that led to dose interruption, serious TEAEs, and TEAEs that resulted in death will be summarized by treatment arm as treated.

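### SAP 8.3.2 defines a treatment-emergent laboratory abnormality by timing alone, so its CTCAE-graded table counts abnormalities already present at baseline that never worsen

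*SAP*

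**What the plan says.** SAP 8.3.2 gives the definition: "The treatment emergent laboratory abnormality is defined as laboratory abnormality reported during the treatment emergent period". It refers the reader to Section 6 for the period, but Section 6 covers treatments and medications. The period is in Section 4.1.6: "The treatment emergent period is defined as the period of time from the date of the first dose of study drug", ending 30 days after the last dose or at the start of new CLL therapy if that is earlier. Section 8.3.2 then sets the scale: "Treatment emergent laboratory abnormality, per NCI CTCAE v4.03 grading, will be summarized for hematology and chemistry laboratory parameters of clinical interest".

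Three other laboratory outputs are planned:

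- SAP 8.3.2 tabulates platelets, hemoglobin and neutrophils by both IWCLL 2008 and CTCAE grade. Under SAP 8.3.1, the IWCLL post-baseline grade for hemoglobin and platelets is a percentage decrease from baseline. For neutrophils, both baseline and post-baseline grades use absolute values.
- SAP 8.3.2 plans a shift table from baseline grade to maximum post-baseline CTCAE grade.
- Protocol 9.7 plans a worst post-baseline grade summary within the treatment-emergent period, for any grade and Grade 3/4, showing the difference in percentages between groups.

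For adverse events, SAP 8.1.1 does address worsening: "Any ongoing event that worsens in severity after the first dose date of study drug is also defined as a TEAE". Protocol 7.2.1 likewise does not treat a pre-existing condition as an adverse event unless it worsens.

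**The concern.** A label of *treatment emergent* tells the reader that something appeared or worsened on drug. Here it would often describe disease. Inclusion criterion 5a accepts as a sign of active disease "Evidence of progressive marrow failure as manifested by the development of, or worsening of, anemia (hemoglobin < 10 g/dL", or platelets below 100,000/µL. Criterion 8 sets the floors at "Platelet count ≥ 30,000"/µL and neutrophils 750/µL, or 500/µL with documented marrow involvement, and lists no hemoglobin floor. Protocol Appendix E says of this population: "A substantial proportion of subjects would be considered to have Grade 2 to 4 hematologic toxicity before any therapy is given".

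What is at stake is the descriptive laboratory safety comparison. Absolute rates in the CTCAE-graded table would be too high in both arms, and a real difference between acalabrutinib and ibrutinib would look smaller.

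**Working it through.** The documents state no figure on this point, so there is none to reproduce. The check has two parts.

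**1. What each planned table does with a baseline cytopenia**

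Take a subject who enters with platelets of 40,000/µL and rises to 60,000/µL.

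| Output | Baseline built in? | Result for this subject |
|---|---|---|
| CTCAE treatment-emergent table (SAP 8.3.2) | No, timing only | Counted: 60,000/µL is still under the SAP 5.3.2 thrombocytopenia cut-off of 100 x 10^9/L |
| IWCLL platelets and hemoglobin (SAP 8.3.1, Appendix E) | Yes, percentage decrease | Grade 0, since there is no decrease |
| CTCAE shift table (SAP 8.3.2) | Yes, shows baseline grade | Visible as no worsening |

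CTCAE cut-offs are not in the documents, so no CTCAE grade is assigned here.

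For neutrophils, take a subject who enters at 800/µL and stays there. The entry floor of 750/µL admits this subject. On the Appendix E scale, 500 to below 1000/µL is Grade 3 before and after first dose, so the IWCLL neutrophil table counts Grade 3 toxicity with no change. Note 4 to Appendix E calls a subject with a pretreatment count below 1000/µL not evaluable for neutrophil toxicity. SAP 8.3 does not carry that rule over.

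One value in the window is enough to be counted. Appendix A schedules hematology weekly for the first 8 weeks, so a persisting baseline abnormality will almost certainly be picked up.

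**2. Size in an any-grade table**

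Let b be the share abnormal at baseline and still abnormal at one or more on-treatment values (equal in both arms), and p the rate of new abnormality among the rest.

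- As written: rate = b + (1-b)p.
- With a worsening rule: rate = p, if baseline-abnormal subjects worsen at the same rate p.
- Difference as written = (1-b)(pA - pB), which is the factor 1-b times the difference under the rule.

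All inputs below are assumed: p = 20% (acalabrutinib) and 30% (ibrutinib), b from 0% to 40%.

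| b | Acalabrutinib | Ibrutinib | Difference (points) | Ratio |
|---|---|---|---|---|
| 0% | 20% | 30% | 10 | 0.67 |
| 10% | 28% | 37% | 9 | 0.76 |
| 20% | 36% | 44% | 8 | 0.82 |
| 30% | 44% | 51% | 7 | 0.86 |
| 40% | 52% | 58% | 6 | 0.90 |

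For example, at b = 20%: 0.20 + 0.80 x 0.20 = 0.36 and 0.20 + 0.80 x 0.30 = 0.44.

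*Sensitivity to the equal-worsening assumption.* If baseline-abnormal subjects worsen at rate q, the rule gives (1-b)p + bq. With b = 20% and q = 25% in both arms, that is 0.16 + 0.05 = 21% against 0.24 + 0.05 = 29%. The difference is 8 points under either definition, and only the ratio changes (0.72 under the rule, 0.82 as written). So the inflation is general, while the loss in the point difference depends on worsening also differing by arm among baseline-abnormal subjects.

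*Grade 3/4.* Here b is only the share already at Grade 3/4 at baseline, which cannot exceed the any-grade share. Protocol 6.2.10.3 gives 23% to 29% for Grade 3 or 4 neutropenia on ibrutinib. Taking 23%, an assumed 13% on acalabrutinib and an assumed b of 10%: 0.10 + 0.90 x 0.13 = 21.7% and 0.10 + 0.90 x 0.23 = 30.7%. The difference goes from 10.0 to 9.0 points.

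**The case against.** The strongest reply is that the authors saw the problem and planned for it. Directly after noting the baseline cytopenias, Appendix E introduces the modified grading scheme for that reason, and SAP 8.3.2 uses it. This stands for hemoglobin and platelets. A reader might infer that admitted cytopenias are counted as emergent throughout the hematology reporting; the documents do not support that. It does not stand for neutrophils, nor for the CTCAE-graded table.

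Second, the shift table lets a reader count subjects whose grade rose. This stands in large part. But the shift table does not correct the incidence table beside it, and it is not stated to use the same window. SAP 4.1.1 treats any value after first dose as post-baseline, and Appendix A continues blood counts at response evaluations after drug is stopped.

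Third, Protocol 9.7 itself plans worst post-baseline grade with no worsening condition, so the SAP follows it. That is a fair defence of tabulating worst grade, but not of calling it treatment emergent.

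Fourth, a reader might infer that chemistry rates are inflated too. The same definition applies to them, but the documents offer no evidence of common baseline chemistry abnormality, and criterion 8 caps transaminases and bilirubin at entry.

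**Conclusion.** The point holds for the CTCAE-graded treatment-emergent table and, through absolute grading, for the IWCLL neutrophil table. Followed as written, both count abnormalities that preceded treatment and did not worsen. Any-grade rates rise from p to b + (1-b)p, and the between-arm difference shrinks by the factor 1-b. This assumes that b is equal in the arms and persists on treatment, and that baseline-abnormal subjects worsen at the same rate as the rest. The size of b is unknown, so the 10% to 40% range is illustrative only.

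Two stronger readings are not supported. Nothing points to a systematic advantage for one arm: randomization should balance b, so the effect is inflation and dilution. Nor is any tested conclusion at risk. The laboratory tables are descriptive and lie outside the gate-keeping sequence of SAP 2.6, and the benefit:risk endpoints in SAP 2.2.2.1 are infections, Richter's transformation, atrial fibrillation and survival. Severity is minor to moderate.

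**What to change.** Replace the definition in SAP 8.3.2 with: *an abnormality in the treatment-emergent period (Section 4.1.6) whose grade is higher than the baseline grade for the same parameter and direction; if baseline is missing, any Grade >= 1 value counts.* This also corrects the reference to Section 6.

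Keep the Protocol 9.7 summary, labelled *worst post-baseline grade*. Keep the shift table and state its window. For the IWCLL neutrophil table, apply the Appendix E statement on subjects with a pretreatment count below 1000/µL, or say why it is not applied.

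The cost is one SAP sentence, one programming condition and a few labels. Baseline CTCAE grades are already needed for the shift table. The downside is that reported incidences become lower.

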### **8.3.3 Analysis of Lymphocytosis**

For all subjects with baseline and any post-baseline absolute lymphocyte count (ALC) measurements, ALC at peak summary will be provided by treatment arm. Median percentage change in ALC from baseline with its 95% CI will also be displayed graphically over time.

CCI [REDACTED]  
[REDACTED]  
[REDACTED] CCI [REDACTED]  
[REDACTED]  
[REDACTED]

CCI  
[Redacted text block]

[Redacted text block]

CCI  
[Redacted text block]

#### **8.3.4 Analysis of Serum Immunoglobulins**

Serum immunoglobulins (IgA, IgG, and IgM) will be summarized using descriptive statistics at each scheduled post-baseline time point. An additional IgG summary to exclude subjects who received IV immunoglobulin on the study will be provided.

#### **8.4 ECOG Performance Status**

The ECOG performance status grade ranges from 0 to 5. The ECOG performance score will be summarized by descriptive statistics. Shift to maximum post-baseline score in ECOG performance score will be summarized by treatment arms.

#### **8.5 Vital Signs and Weight**

Body temperature, pulse rate (beats/min), systolic and diastolic blood pressure (mmHg), respiratory rate (breaths/min), and weight (kg) will be summarized. Systolic and diastolic blood pressure will be graded using NCI CTCAE v4.03. Shift to maximum post-baseline score will be summarized for blood pressure parameters by treatment arms.

#### **8.6 Electrocardiogram**

Subject incidence of ECG abnormality at baseline and post-baseline visits will be summarized by treatment arms. Number and percentage of subject with QTcB or QTcF values >480 msec at screening visit will be summarized in a table.

9 [CCI] [REDACTED]

[CCI] [REDACTED]  
[REDACTED]  
[REDACTED]

9.1 [CCI] [REDACTED]

[CCI] [REDACTED]

9.1.1 [CCI] [REDACTED]

[CCI] [REDACTED]  
[REDACTED]  
[REDACTED]

[REDACTED]  
[REDACTED]  
[REDACTED]  
[REDACTED]  
[REDACTED]

[REDACTED]

[REDACTED]

[REDACTED]

[REDACTED]

[REDACTED]

[REDACTED]

9.1.2 [CCI] [REDACTED]

[CCI] [REDACTED]  
[REDACTED]  
[REDACTED]  
[REDACTED]  
[REDACTED]  
[REDACTED]  
[REDACTED]  
[REDACTED]  
[REDACTED]  
[REDACTED]

**9.2** CCI [Redacted]

CCI [Redacted]

[Redacted]

**9.2.1** CCI [Redacted]

CCI [Redacted]

[Redacted]

**9.2.2** CCI [Redacted]

CCI [Redacted]

[Redacted]

[Redacted]

[Redacted]

[Redacted]

**9.2.3** CCI [Redacted]

CCI [Redacted]

[Redacted]

**9.2.4** CCI [Redacted]

CCI [Redacted]

[Redacted]

[Redacted]

[Redacted]

## 11 APPENDIX

### APPENDIX 1 – Definition of Adverse Event of Special Interest and Events of Clinical Interest (MedDRA version 23.0)

#### 1. Adverse Event of Special Interest (AESI)

The following preferred terms (PT) for the ventricular arrhythmias AESI include:

- Torsade de pointes
- Ventricular arrhythmia
- Ventricular extrasystoles
- Ventricular fibrillation
- Ventricular flutter
- Ventricular tachyarrhythmia
- Ventricular tachycardia

#### 2. Events of Clinical Interest

The Events of Clinical Interest (ECIs) have been identified based on preclinical findings, emerging data from clinical studies relating to acalabrutinib, and pharmacological effects of approved Bruton's tyrosine kinase (BTK) inhibitors. The adverse events (AEs) selected for dedicated analysis were evaluated using Standardized MedDRA Queries (SMQs), where available, by System Organ Classes (SOCs), or by Sponsor-defined baskets of MedDRA Adverse Event Grouped Terms.

Category	Subcategory	Definition
Cardiac events	Atrial fibrillation	
 
• SOC Cardiac disorders
 
• PT Atrial fibrillation
 
• PT Atrial flutter
 

	Ventricular tachyarrhythmias	
 
• PT Torsade de pointes
 
• PT Ventricular fibrillation
 
• PT Ventricular flutter
 
• PT Ventricular tachyarrhythmia
 
• PT Ventricular tachycardia
 

Cytopenias – Anemia		
 
• SMQ Haematopoietic erythropenia [narrow + broad]
 

Cytopenias – Leukopenia	Neutropenia	
 
• SMQ Haematopoietic leukopenia [narrow + broad]
 
• PT Band Neutrophil count decreased
 
• PT Band neutrophil percentage decreased
 
• PT Cyclic neutropenia
 
• PT Febrile Neutropenia
 
• PT Idiopathic neutropenia
 
• PT Neutropenia
 
• PT Neutropenic infection
 
• PT Neutropenic sepsis
 
• PT Neutrophil count decreased
 
• PT Neutrophil percentage decreased
 

	Other leukopenia	
 
• SMQ Haematopoietic leukopenia [narrow + broad] excluding PTs for neutropenia above
 

Cytopenias - Thrombocytopenia		
 
• SMQ Haematopoietic thrombocytopenia [narrow + broad]
 

Hemorrhage	
 
SMQ Haemorrhage terms (excl laboratory terms)
 

Major hemorrhage	
 
As per definition (see Section 3 below)
 

Hepatotoxicity	
 
SMQ [narrow] Hepatic failure, fibrosis and cirrhosis and other liver damage-related conditions
 
SMQ [narrow] Hepatitis, non-infectious
 
SMQ [narrow] Liver related investigations signs
 

Hypertension	
 
SMQ Hypertension [narrow]
 

Infections	
 
SOC Infections and infestations
 

Interstitial lung disease/Pneumonitis	
 
SMQ [narrow] Interstitial lung disease
 

Second primary malignancies	
 
SMQ Malignant tumours (including Haematological malignant tumours SMQ and Non-haematological malignant tumours SMQ)
 
SMQ Malignant lymphomas [narrow]
 
SMQ Myelodysplastic syndrome [narrow]
 

Second primary malignancies (excluding non melanoma skin)	
 
The above excluding PTs mapping to HLT Skin neoplasms malignant and unspecified (excluding melanoma)
 

Tumor lysis syndrome	
 
PT Tumour lysis syndrome
 

HLT=High-Level Term; PT=Preferred Term; SOC=System Organ Classes; SMQ=Standardized MedDRA Queries.

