7.2.1 Definitions

Adverse Events

An AE is any untoward medical occurrence in a subject administered a pharmaceutical product and which does not necessarily have a causal relationship with this treatment. An AE can therefore be any unfavorable and unintended sign (including a clinically significant abnormal laboratory finding, for example), symptom, or disease temporally associated with the use of an investigational study drug, whether or not considered related to the study drug ([FDA Guidance for Industry 1995](#)).

For the purposes of this clinical study, AEs include events which are either new or represent detectable exacerbations of pre-existing conditions.

Disease progression is not an AE; rather it may be the cause of an AE. The clinical diagnosis that is associated with disease progression must be reported as all other AEs. "Disease progression" should never be used as an AE term.

AEs may include, but are not limited to:

- Subjective or objective symptoms spontaneously offered by the subject and/or observed by the Investigator or study staff including laboratory abnormalities of clinical significance (Note: "clinical significance" is defined as requiring change in study drug dose or discontinuation of study drug or any other medical intervention).
- Any AEs experienced by the subject through the completion of final study procedures.
- AEs not previously observed in the subject that emerge during the protocol-specified AE reporting period, including signs or symptoms associated with CLL that were not present before the AE reporting period.

The following are NOT considered an AE:

- **Pre-existing condition:** A pre-existing condition (documented on the medical history CRF) is not considered an AE unless the severity, frequency, or character of the event worsens during the study period.

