7.2.2.4 Second Primary Malignancies

Adverse events (AEs) for malignant tumors reported during a study should generally be assessed as serious AEs (SAEs). If no other seriousness criteria apply, the “Important Medical Event” criterion should be used. In certain situations, however, medical judgment on an individual event basis should be applied to clarify that the malignant tumor event should be assessed and reported as a nonserious AE. For example, if the tumor is included as medical history and progression occurs during the study but the progression does not change treatment and/or prognosis of the malignant tumor, the AE may not fulfill the attributes for being assessed as serious, although reporting of the progression of the malignant tumor as an AE is valid and should occur. Also, some types of malignant tumors, which do not spread remotely after a routine treatment that does not require hospitalization, may be assessed as nonserious; examples in adults include Stage 1 basal cell carcinoma and Stage 1A1 cervical cancer removed via cone biopsy.

The above instruction applies only when the malignant tumor event in question is a new malignant tumor (i.e., it is not the tumor for which entry into the study is a criterion and that is being treated by the IP under study and is not the development of new or progression of existing metastasis to the tumor under study). Malignant tumors that—as part of normal, if rare, progression—undergo transformation (e.g., Richter's transformation of B cell chronic lymphocytic leukemia into diffuse large B cell lymphoma) should not be considered a new malignant tumor.

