### **8.1.2 Adverse Events of Clinical Interest**

Adverse events of clinical interest (ECIs) are specified in Appendix 1 and are to be reported for the duration of study treatment and during any protocol-specified follow-up periods, including post-disease progression phase for overall survival. These events will be summarized similarly to TEAEs by treatment arm.

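### SAP Appendix 1 defines second primary malignancies without excluding the study CLL or its Richter's transformation, so a descriptive safety rate may count transformations as new cancers

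*SAP*

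**What the plan says.** SAP Appendix 1, Section 2 (Events of Clinical Interest) has two rows for second primary malignancies. The first combines three queries: "SMQ Malignant tumours (including Haematological malignant tumours SMQ and Non-haematological malignant tumours SMQ", then "SMQ Malignant lymphomas [narrow" (narrow terms only), then the narrow myelodysplastic syndrome query. It has no exclusion. The second row has one: "The above excluding PTs mapping to HLT Skin neoplasms malignant and unspecified (excluding melanoma".

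On how these events are presented, SAP 8.1.2 says "These events will be summarized similarly to TEAEs by treatment arm". It describes no step at which a case is reviewed and removed.

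Protocol 7.2.2.4, which has the same title as the SAP category, applies its instruction only to a new malignant tumor. It specifies that "it is not the tumor for which entry into the study is a criterion", and that transformation of the CLL "into diffuse large B cell lymphoma) should not be considered a new malignant tumor".

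Protocol 7.2.1 bars disease progression as an adverse event term but adds: "The clinical diagnosis that is associated with disease progression must be reported as all other AEs". Protocol 7.2.2.7 asks for deaths to be reported with the primary cause of death as the event term.

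Richter's transformation is also a secondary endpoint in its own right. It is assessed by central pathology (SAP 7.2.1) and stands third in the fixed testing sequence (SAP 2.6).

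**The concern.** The same label has two meanings. In the protocol, a transformation of the study disease is not a second malignancy. In the SAP, any event whose coded term falls in the tumour or lymphoma queries is one. If Richter's cases are coded as lymphoma, they would be tabulated as new cancers.

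This matters more here than in most trials because Richter's transformation is expected to occur and may differ by arm. Protocol 1.1 cites a high rate on ibrutinib in 17p del disease, and Protocol 2.3 states the hypothesis that a more selective inhibitor may lower it. Any difference in Richter's would then also appear, under another name, in the second-primary-malignancy rate, where it could be misread as a difference in new cancers.

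**Working it through.** The plan gives no figure to reproduce. The check is a comparison of texts, followed by a rough scale.

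**Comparison of texts**

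1. *Is an exclusion written anywhere?* Not in either Appendix 1 row, and not in SAP 8.1.2. SAP Appendix 2 repeats the same queries for narratives, again removing only non-melanoma skin terms.
2. *Does the protocol treat these events as new malignancies?* No. Protocol 7.2.2.4 sets aside both the tumor required for entry and its transformation.
3. *Can such events reach the adverse event data?* Yes. Protocol 7.2.1 has the diagnosis behind progression reported, and Protocol 7.2.2.7 has the cause of death reported. Protocol 7.2.2.4 says how a transformation is to be classed; it does not say that it goes unreported.
4. *Would the queries pick them up?* Probably, judging from query names that expressly cover haematological malignancies and lymphomas. The term lists and the coding of Richter's are not in the documents, so this step is inferred.

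**Scale, for Richter's only**

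Inputs:
- Richter's rate on ibrutinib in 17p del disease: 11/144, median follow-up 13 months (Protocol 1.1).
- Share of subjects with 17p del, taken from the historical trial's subgroup sizes of 127 and 122 (SAP 2.3, Table 1), overlap ignored: 127/(127 + 122) = 51.0%.
- Subjects per arm: 250 (Protocol 9.3).
- Assumed: no Richter's in subjects with 11q del only.

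Formula: added cases per 250 = 250 × rate × 17p share × fraction captured.

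- Point rate: 11/144 = 7.64%. Full capture gives 250 × 0.0764 × 0.510 = 9.7, or 3.9% of the arm.
- Exact 95% CI of 11/144: 3.87% to 13.26%. Full capture gives 4.9 to 16.9.
- 17p share of 40% or 60% at the point rate: 7.6 or 11.5.
- Half capture: 4.9 (2.5 to 8.5 over the CI).
- No capture: 0.

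The result depends on the assumptions. If subjects with 11q del only had the same rate as those with 17p del, the point figure would be 250 × 11/144 = 19.1.

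For comparison, Protocol 6.2.10.6 gives 3% to 16% for other malignancies on ibrutinib, which is 7.5 to 40 per 250. Whether that range includes Richter's is not stated.

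No document gives a Richter's rate for acalabrutinib, so no arm difference can be estimated.

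**The case against.** The strongest reply is that only an unwritten exclusion has been shown, not an inflated rate. Capture depends on term lists and coding that are not in the documents, and the count could be zero. This stands, and it is why the size is given as a range that starts at 0.

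Second, the table may reveal its own content. SAP 8.1.2 has these events summarized like treatment-emergent events, and SAP 8.1.1 shows those by preferred term. Lymphoma lines would then be visible. This also stands. What remains exposed is the top-line percentage, together with the question of whether a given lymphoma line is a transformation or a true second cancer.

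Third, Protocol 7.2.2.4 concerns how sites assess and report malignancies, not how they are analysed, and a broad safety query is a legitimate choice. That is fair as far as it goes. It is nevertheless the protocol's only statement of what counts as a new malignant tumor, and a deliberately broad category should not carry the narrower label without saying so.

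Fourth, the route for CLL terms is weaker than the route for Richter's, because progression itself may not be used as an event term. The numbers above therefore concern Richter's only.

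A reader might also infer a mismatch of time windows. SAP 8.1.2 has these events reported through follow-up, "including post-disease progression phase for overall survival", while the Richter's endpoint is treatment-emergent, so subtracting one count from the other would not recover the right figure. The documents do not support that inference:
- The SAP sentence concerns reporting; the summary itself follows the treatment-emergent tables.
- Protocol 7.2.2.1 limits late reporting to serious events or other events of concern believed related to study drug.
- Protocol Section 4 records additional malignancies after progression, which under Protocol 7.2.2.4 does not clearly cover a transformation.

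**Conclusion.** The point holds in a limited form. As written, both Appendix 1 rows would count a lymphoma-coded Richter's transformation, or any CLL-coded event, as a second primary malignancy, contrary to the protocol's own statement of what is new. This is a stated rule that can give a mislabelled rate, not merely a missing detail.

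The consequence is confined to a descriptive by-arm safety table. The non-inferiority test of PFS, the OS analysis and the tested Richter's endpoint do not use these rows. The size is anywhere from 0 to roughly 17 cases per 250, assuming the cited 17p del ibrutinib rate with its sampling uncertainty, a 51% 17p share, no cases in subjects with 11q del only, and capture between none and full.

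A reader might go further and conclude that the table will favour one arm. The documents do not support this: they state a hypothesis about Richter's but give no acalabrutinib rate. The change is worth making because it is cheap and specific, and because deciding after unblinding which lymphomas count would be harder to defend in an open-label trial. Confidence is medium, limited by the unseen term lists and coding.

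**What to change.** Before sponsor unblinding, amend both second-primary-malignancy rows of SAP Appendix 1 to exclude events that are the study CLL or its Richter's transformation:

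- Give a list of preferred terms for the study disease and its transformation.
- Match lymphoma-coded events, case by case, to the centrally assessed Richter's cases of SAP 7.2.1, so that a true second lymphoma stays in the table.
- State the default classification where central pathology is missing.

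The wording in Appendix 2 can be aligned for consistency. Little depends on it, because narratives already cover all deaths, serious events and events leading to discontinuation of study drug.

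The cost is a few lines of SAP text, a term list and the case-level match, with no new data collection. The downside is small: the default for cases without central pathology may misclassify a few events.
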